#### *Neuroendocrine prostate cancer (NEPC)*

NEPC develops *de novo* in some patients and in up to 15–20% of patients with metastatic prostate cancer treated with androgen deprivation therapy. In a review of 87 patients with NEPC retrospectively identified at Weill Cornell Medicine (WCM) between 2004 and 2017, 75% of patients with *de novo* NEPC and 92% of patients with treatment related NEPC had liver metastases at the time of diagnosis of NEPC, respectively (Eur J Cancer . 2019 Nov;121:7-18). Dependence on androgen receptor (AR) signaling is lost as tumors progress from a prostate adenocarcinoma to a NEPC histology, typically manifest by downregulation of AR, PSA, and PSMA expression in tumors (Curr Oncol Rep. 2021 Jan 12; 23(2):15). Genomic analyses from patient biopsies combined with preclinical modeling has pointed to loss of tumor suppressors RB1 and TP53 as important genomic events that contribute to NEPC development. Treatment related NEPC is resistant to most therapies and has a poor prognosis with a median survival of less than one year from diagnosis.

## **2.2 Investigational Agent**

Cabozantinib is a kinase inhibitor that targets receptor tyrosine kinases including MET, VEGFR -1 (Flt-1), VEGFR-2 (KDR) and VEGFR-3 (Flt-4), RET, KIT, TRKB, FLT-3, AXL, and TIE-2 with variable potencies (Table1; [27]). These receptor tyrosine kinases are involved in both normal cellular function and pathologic processes such as oncogenesis, metastasis, tumor angiogenesis, drug resistance, and maintenance of the tumor microenvironment. Cabozantinib is FDA approved for treatment in renal cell carcinoma and medullary thyroid cancer.

**Table 1.** *In vitro* kinase inhibition profile of cabozantinib

Kinase	IC 50 ± SD, a nmol/L	Enzyme concentration, nmol/L	ATP concentration, μmol/L	Assay
VEGFR2	0.035 ± 0.01	0.05	3	A
MET	1.3 ± 1.2	10	1	C
MET (Y1248H)	3.8	13	1	C
MET (D1246N)	11.8	12	1	C
MET (K1262R)	14.6	12	1	C
RET	5.2 ± 4.3	15	2	C
TIE2	14.3 ± 1.1	15	5	R
AXL	7	TBD	TBD	TBD
FLT3	11.3 ± 1.8	0.5	1	C
KIT	4.6 ± 0.5	1	3	A
RON	124 ± 1.2	60	1	C

Abbreviations: A, AlphaScreen; C, Coupled luciferase; R, radiometric; TBD, to be determined.

aMean ± SD of at least 3 independent determinations.

### 2.2.1 Cabozantinib in prostate cancer

#### Preclinical activity

Inhibition of the kinase targets of cabozantinib has been shown to affect both osteoblast and osteoclast activity, limiting the growth of bony lesions in xenograft models of mCRPC [28]. Earlier *in vitro* work illustrated that androgen-insensitive PC cell lines had greater c-MET ligand HGF expression versus androgen-dependent lines and, furthermore, deprivation of androgen caused upregulation of c-MET [15]. Understanding of the *in vivo* mechanism has further been enhanced, with demonstration that the drug's effect may be potentiated by interactions with immune and bony microenvironments, and data revealing a more dramatic effect *in vivo* than *in vitro*. For example, Patnaik et al. demonstrated that cabozantinib eliminated invasive PTEN-/p53- mouse model only when chemotaxis of neutrophils was left intact [29]. Additionally, cabozantinib increases Treg infiltration, immune recognition, and T-cell mediated killing by upregulating MHC-1 molecules and markers (*e.g.* ICAM-1, Fas) in a VEGFR2- and MET-expressing cell line [30]. Furthermore, cabozantinib alone or in combination with immune checkpoint blockade decreases myeloid-derived suppressor cells (MDSCs), which are associated with a tumor permissive microenvironment, which increases immune surveillance [31, 32]. Design and interpretation of future studies must recognize that interactions with the immune and tumor microenvironment may potentiate drug effects.

#### Clinical studies

Based on preclinical data suggesting cabozantinib had anti-tumor activity in PC, a series of Phase I and II clinical trials were performed in unselected patients with CRPC and demonstrated that cabozantinib treatment in patients with CRPC resulted in high rates of pain relief and reductions in or discontinuations of narcotic use, along with evidence of substantial anti-tumor activity including bone scan resolution, soft-tissue lesion reduction and 12-week disease control [33]. In one phase II randomized discontinuation trial in patients with CRPC, 72% of patients exhibited regression in soft-tissue lesions, whereas 68% of patients had improvement in technetium-99m bone scan response, including complete resolution in 12%. The trial exhibited a median progression-free survival (PFS) of 23.9 versus 5.9 weeks for the cabozantinib and placebo-treated cohorts, respectively, with significant reductions in bone turnover markers and bone pain with cabozantinib treatment [28].

These observations led to the phase III multicenter, randomized COMET-I trial to evaluate the effect of cabozantinib compared to prednisone in men with previously treated metastatic CRPC. These patients had bone-dominant disease and exhibited disease progression on docetaxel-containing

chemotherapy and abiraterone or enzalutamide with the primary endpoint being overall survival (OS)[34]. No molecular markers were assessed in PC tissue or bone to determine if a molecular target of cabozantinib was amplified or mutated. A total of 1,028 patients were randomly assigned to cabozantinib (n = 682) or prednisone (n = 346). The primary endpoint of improvement in OS was not met with the median OS 11.0 months with cabozantinib and 9.8 months with prednisone (hazard ratio, 0.90; 95% CI, 0.76 to 1.06; stratified log-rank p = 0.213). Analysis of secondary endpoints however showed (1) radiographic progression free survival (rPFS) was improved in the cabozantinib group (median, 5.6 v 2.8 months; hazard ratio, 0.48; 95% CI, 0.40 to 0.57; stratified log-rank p < 0.001); (2) the favorable CTC conversion rate (defined as > five CTCs at baseline to < five CTCs as best post baseline result) was 33% for cabozantinib and 6% for prednisone; and (3) Bone scan response at week 12 per an independent radiology review committee was 42% (95% CI, 38% to 46%) with cabozantinib and 3% (95% CI, 1% to 5%) with prednisone (unstratified and stratified Cochran-Mantel-Haenszel p < 0.001 for both).

Cabozantinib was not associated with improved PSA response or time to PSA progression. A PSA response, defined as a reduction of 50% or more in PSA level, occurred in 6% of cabozantinib-treated patients and 2% of prednisone-treated patients. The median time to PSA progression was 4.2 and 3 months with cabozantinib and prednisone, respectively (unstratified HR, 0.95; p = 0.639). Because COMET-1 failed to meet its primary endpoint, further development of cabozantinib in the treatment of men with CRPC was halted, and another trial, COMET-2 focused on pain palliation as the primary endpoint for cabozantinib versus mitoxantrone-prednisone in patients with symptomatic bone metastases using patient-reported outcome measures. The study was discontinued after 119 patients were randomized. In this study, cabozantinib did not demonstrate better pain palliation than mitoxantrone-prednisone in heavily pretreated patients with mCRPC and symptomatic bone metastases[35]. A recent analysis of pooled data from patients enrolled on COMET-1 and COMET-2 trials demonstrated that, after adjusting for prognostic factors, cabozantinib use was associated with better overall survival (hazard ratio 0.80, 95% confidence interval 0.67–0.95; p = 0.012)[36].

The CONTACT-02 study was a phase 3 pivotal study evaluating cabozantinib in combination with atezolizumab compared with a second novel hormonal therapy in patients with mCRPC and measurable extra-pelvic soft tissue disease who have progressed on one prior ADT. Results presented at ASCO GU in January 2024 showed that at a median follow-up of 14.3 months, the median PFS was 6.3 months for cabozantinib in combination with atezolizumab compared with 4.2 months for second line novel hormonal therapy (hazard ratio (HR) was 0.65 (95% confidence interval [CI]: 0.50-0.84; p=0.0007). At a median follow-up of 12.0 months for the ITT population, the median overall survival was 16.7 months for cabozantinib in combination with atezolizumab compared with 14.6 months for second novel hormonal therapy (HR: 0.79; 95% CI: 0.58-1.07; p=0.13). Most impressive was the cohort of patients with liver metastases where the median PFS was 6.2 months for the combination of cabozantinib and atezolizumab compared with 2.1 months in patients receiving a second novel hormonal therapy (HR 0.43 (0.27-0.68). The OS was 16.4 months versus 9.8 months (HR 0.60 (0.35-1.02) in the treatment and control arms, respectively. These data suggest that patients with liver metastases are more likely to respond to cabozantinib. The contribution of atezolizumab to the prolonged rPFS is unclear. Of note, in the CONTACT-02 study, liver biopsies were not performed so it is unknown if any patients had NEPC in their liver metastases.

## 2.3 Rationale

Despite the fact that dramatic improvements in bone scans and pain were observed in some patients with cabozantinib in the COMET-1 and 02 trials, it is unclear why secondary endpoints, including most notably rPFS, did not translate into improved OS. This fact may reflect that unselected patients with relatively insensitive tumors were included in the study population, given that the subjects were not

evaluated for the presence of amplifications of or activating mutations in gene targets of cabozantinib prior to enrollment. Increasing availability of genomic analyses of metastatic PC specimens and/or cell free tumor derived DNA makes possible selection of study subjects with presumed dependence on cabozantinib targets (*i.e.*, presence of amplifications or activating mutations). Analysis of expression profiling of metastatic PC specimens from Weill Cornell has shown increased expression of cabozantinib's target genes MET and KIT in a significant percentage of metastatic tumors (unpublished data). VEGF alterations are found in 1-4% by DNA amplification and as much as >5% by RNA overexpression. Additionally, publically available data report the presence of mutually-exclusive qualifying mutations or activating mutations in ~17% of patients (SU2C mCRPC cohort). We predict that targeting a molecularly-defined patient cohort will identify the patient population that most benefits from cabozantinib therapy, as reflected in prolonged rPFS and OS, and more frequent PSA declines and CTC conversions.

## **2.4 Risk/Benefit Assessment**

This is a phase II clinical trial with the primary endpoint to assess rPFS in a genomic target-selected patient population. Based on prior experience of treating unselected CRPC patients with cabozantinib, we anticipate that a significant proportion of patients that are biomarker-selected or have liver metastases will benefit from cabozantinib therapy. The expected toxicities include diarrhea, high blood pressure, hand-foot

syndrome, fatigue, nausea, decreased appetite, and painful mouth sores. It is noted with any molecular test, like those proposed to gain molecular qualification for this trial, has implicit risks of false positive results. In this case a subject may forego alternative therapies under the apprehension of possible enhanced likelihood of benefit from cabozantinib. The Informed Consent Form includes discussion of such risks.

## **2.5 Correlative Studies Background**

### *Cell-free DNA*

Measurement of cell-free or circulating tumor DNA (ctDNA) in plasma is a noninvasive method to molecularly analyze and characterize a patients' tumor. In addition, it allows repeated longitudinal sampling. In the current study, we aim to define the spectrum and frequency of genomic changes found in plasma DNA of patients with mCRPC prior to cabozantinib therapy and determine types and frequencies of genomic mutations that arise with treatment. In collaboration with [name], we will collect plasma samples and then analyze them using the PCF SELECT (Specific Evaluation in Liquid biopsies of Established prostate Cancer Targets) plasma ctDNA assay. This is a custom designed prostate cancer specific panel including 74 target genes, 42 control genes covering both exonic regions and informative single nucleotide polymorphisms (SNPs) optimized for the detection of CRPC aberrations including estimation of copy number in ctDNA. PCF SELECT (tumor DNA from cfDNA and germline control) will be run at baseline, on therapy (at 3 months), and at clinical progression.

### *Immune Biomarkers*

Preclinical studies in a PTEN/p53-deficient murine PC model showed that cabozantinib rapidly eradicated poorly differentiated tumors [29]. This anti-tumor effect was associated with enhanced release of neutrophil chemotactic factors from tumor cells, predominantly CXCL12 - resulting in robust infiltration of neutrophils into the tumor. This study suggested that cabozantinib triggered a neutrophil-mediated anticancer innate immune response.

Cabozantinib also increased Treg infiltration, immune regulation, and T-cell mediated killing by upregulating MHC-I molecules and markers (*e.g.* ICAM-1, Fas) in a VEGFR2- and MET-expressing cell line [30]. Furthermore, cabozantinib alone or in combination with immune checkpoint blockade decreases myeloid-derived suppressor cells (MDSCs), which are associated with a tumor permissive

microenvironment, which increases immune surveillance [31, 32].

In order to test the systemic effects of cabozantinib treatment in PC patients on immune signals and cytokines related to possible immunity-dependent effects of cabozantinib, we will assess gene expression and immune cell infiltrates at baseline and after initiation of cabozantinib treatment. We will also measure circulating levels of cytokines. The primary hypothesis will be that treatment will reduce systemic levels of cytokines associated with a suppressive myeloid microenvironment. To that end, we will quantify pre and on treatment levels of the following cytokines: interleukin-8, interleukin-6 and interleukin-1 all of which have been associated with a non-permissive tumor microenvironment. As a secondary hypothesis, we will test whether levels of pro-inflammatory cytokines are increased in a compensatory manner – those studies will focus on the TH1 cytokines particularly interferon gamma, interleukin-12 and interleukin-2. Of note, prior studies by our group suggested that a TH1 cytokine signature was associated with a decreased risk of prostate cancer progression in a population-based study.

### **3. STUDY DESIGN**

#### **3.1 Overall Design**

The hypothesis for this trial is that cabozantinib has anti-tumor activity in a molecularly-selected group of patients with CRPC or patients with liver metastases. This is a single-arm, open-label Phase II multi-institutional trial in 30 patients that have been molecularly selected based on that their tumors possess alterations in molecular targets of cabozantinib. Patients will be treated continuously until they develop radiographic progression or discontinue cabozantinib for toxicity. If 6 or more out of 12 subjects with particular mutation or gene amplification show progression prior to 6 months, accrual for the particular genomic alteration may close. In addition, a series of correlative studies will be performed including tissue biopsies in order to further define the mechanisms of cabozantinib anti-tumor action in prostate cancer and identify surrogate markers of response.

#### **3.2 Scientific Rationale for Study Design**

Cabozantinib has demonstrated anti-tumor efficacy in a significant proportion of unselected patients with mCRPC. Testing the effect of cabozantinib in an enriched patient population with an alteration in a molecular target of cabozantinib may increase the objective response rate. In addition, a proportion of patients with liver metastases appear to benefit from cabozantinib. Identifying biomarkers in liver metastases which correlate with response to cabozantinib would allow more rationale and targeted patient selection.

#### **3.3 Justification for Dose**

The FDA approved dose for cabozantinib for other approved indications is 60 mg, but recent data from Exelixis indicates efficacy at 40 mg daily in men with castrate resistant prostate cancer. Dose reductions for toxicity will follow established guidelines.

#### **3.4 End of Study Definition**

A participant is considered to have completed the study if he or she has completed all phases of the study including the last visit or the last scheduled procedure shown in the Schedule of Assessments (SoA), Section 6.1. The end of the study is defined as completion of the last visit or procedure shown in the SoA in the trial globally.

## 4. SUBJECT SELECTION

### 4.1 Study Population

Men with metastatic CRPC who have had disease progression following prior AR pathway-directed therapy and who meet the inclusion and exclusion criteria will be eligible for participation in this study.

### 4.2 Inclusion Criteria

1. Age >18 years.
2. Documented histological or cytological diagnosis of prostate carcinoma.
3. Evidence of metastatic PC on imaging (bone scan and/or CT/MRI scan)
  - a. Patients with liver metastases must have biopsy proven evidence of metastatic prostate cancer in the liver
4. Agree to undergo a biopsy of at least one metastatic site or primary prostate prior to beginning therapy. Adequate archival metastatic tissue can be used if available in lieu of a biopsy if done when patient had CRPC and within 6 months the start of treatment.
5. Agree to undergo a biopsy of at least one metastatic site or primary prostate after 3 weeks of therapy (biopsy must be between day 21 and day 24 of treatment). Re-biopsy of same pre-treatment biopsy soft tissue site especially liver metastases is preferred.
6. Serum testosterone level less than 50 ng/dL. Subjects without prior orchiectomy must be currently taking and willing to continue luteinizing hormone-releasing hormone (LHRH) analogue (agonist or antagonist) therapy until permanent discontinuation of study treatment.
7. Documented progressive metastatic CRPC based on at least one of the following criteria:
  - a. PSA progression according to Prostate Cancer Working Group 3 (PCWG3) criteria
  - b. Objective radiographic progression, according to PCWG3 criteria
8. ECOG performance status of 0-1
9. Recovery to baseline or  $\leq$  Grade 1 CTCAE v4 from toxicities related to any prior treatments, unless specified below or AE(s) are clinically nonsignificant and/or stable on supportive therapy.
10. Adequate organ and marrow function, based upon meeting all of the following laboratory criteria **within 14 days before first dose of study treatment**:
  - a. Absolute neutrophil count (ANC)  $\geq 1500/\text{mm}^3$  ( $\geq 1.5 \text{ GI/L}$ ) without granulocyte colony-stimulating factor support
  - b. White blood cell count  $\geq 2500/\text{mm}^3$  ( $\geq 2.5 \text{ GI/L}$ )
  - c. Platelets  $\geq 100,000/\text{mm}^3$  ( $\geq 100 \text{ GI/L}$ ) without transfusion.
  - d. Hemoglobin  $\geq 9 \text{ g/dL}$  ( $\geq 90 \text{ g/L}$ )
  - e. Total bilirubin  $\leq 1.5 \times \text{ULN}$  (for subjects with Gilbert's disease  $\leq 3 \times \text{ULN}$ )
  - f. Serum albumin  $\geq 2.8 \text{ g/dL}$
  - g. Serum creatinine  $\leq 2.0 \times \text{ULN}$  or calculated creatinine clearance  $\geq 30 \text{ mL/min}$  ( $\geq 0.5 \text{ mL/sec}$ ) using the Cockcroft-Gault equation:
    - i. If urine dipstick is positive, then:
      1. Urine protein/creatinine ratio (UPCR)  $\leq 1 \text{ mg/mg}$  ( $\leq 113.2 \text{ mg/mmol}$ )
11. Patients without liver metastases must have evidence of amplification or activating mutation of selected targets of cabozantinib (including MET, KIT, RET, VEGFR-1, VEGFR-2, VEGFR-3, FLT3, AXL, TRKB, or TIE2) by **at least one** of the following (See Section 4.4 for full detail):
  - a. DNA sequencing of metastatic tumor biopsy specimen or cfDNA test
  - b. RNA sequencing of metastatic tumor biopsy specimen
  - c. Commercial cell-free DNA assay
  - d. Overexpression by IHC on metastatic tumor biopsy specimen

12. Sexually active fertile subjects and their partners must agree to use medically accepted methods of contraception (*e.g.*, barrier methods, including male condom, female condom, or diaphragm with spermicidal gel) during the course of the study and for 4 months after the last dose of study treatment
13. Capable of understanding and complying with the protocol requirements and must have signed the informed consent document.

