### 1.2.1 Primary Objectives

To assess the radiographic response proportion of cabozantinib in patients with metastatic CRPC who have progressed on an androgen receptor signaling inhibitor whose tumor possess a molecular abnormality that is targeted by cabozantinib or who have liver metastases.

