#### 4.4 Molecular Eligibility

To be eligible, a patient's tumor must have evidence of gene amplification, an activating mutation, or overexpression of one of the following genes: MET, KIT, RET, VEGFR-1, VEGFR-2, VEGFR-3, FLT3, AXL, TRKB, or TIE2. In the event of activating mutations, the observed mutation must be of Level 1, Level 2, or Level 3 as annotated by OncoKB ([www.oncokb.org](http://www.oncokb.org)). Eligibility can be met by **at least one** of the following diagnostic tests:

- 1) DNA sequencing of a metastatic tumor biopsy specimen showing gene amplification or activating mutation using a CLIA-certified assay. Tumor tissue samples must have been collected within 6 months of enrollment.
- 2) Protein overexpression in a metastatic tumor biopsy specimen determined by immunohistochemistry (IHC) showing 3+ protein expression using a CLIA-certified assay. These

- include common in-house KIT and commercial reference labs for panTRK (*e.g.* NeoGenomics) and cMET (*e.g.* NeoGenomics, Caris, Mayo Clinic).
- 3) CLIA-certified commercial cell free DNA assay (either Guardant360 or FoundationOneLiquid assay) reporting gene amplification or activating mutation *within 6 months of enrollment*.
    - a. For the Guardant360 Liquid Biopsy amplification must be at least (++) or (+++) for to meet eligibility.
    - b. For the FoundationOneLiquid assay, amplification will be eligible. Reports that have an “equivocal” or “subclonal” designation will not be eligible.
  - 4) Any non-CLIA certified assay such as RNA expression profiling of a metastatic tumor biopsy specimen showing overexpression must be confirmed by a CLIA-certified assay (*i.e.*, immunohistochemistry showing 3+ protein expression)

Patients who do not meet molecular eligibility criteria will be allowed to enroll if they have liver metastases that meet RECIST criteria for measurable disease. Patients with prostate adenocarcinoma or NEPC will be allowed to enroll.

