### **10.2 Measurable soft-tissue lesions**

When evaluating soft-tissue lesions, the following PCWG-modified RECIST response criteria for target(soft-tissue) lesions definitions apply.

- Complete response (CR): the disappearance of clinical and radiological evidence of all target lesions and normalization of tumor marker levels
- Partial response (PR): a decrease from baseline  $\geq 30\%$  in the sum of the LD of all target lesions
- Progressive disease (PD): an increase  $\geq 20\%$  in the sum of the LD of all target lesions based on the smallest sum LD since treatment started or the appearance of one or more new lesions or the appearance of new lesions
- Stable disease (SD) : neither sufficient shrinkage to qualify for PR nor sufficient increase to qualify for PD based on the smallest sum LD recorded since treatment started

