### **12.1 Study Design/Endpoints**

The proposed design is a single-arm, open-label, non-randomized study. The primary endpoint is radiographic progression-free survival (rPFS) defined as the time from initiation of treatment to minimum of radiographic progression or death, whichever occurs first. We will enroll up to 28 patients with liver metastasis aimed to estimate the rPFS survival probabilities. Using the Kaplan-Meier estimator, with this sample size, we estimate the 95% CI of the median survival probability is 31.1-68.9%

Secondary endpoints include PSA decline, tumor response, and OS.

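### Sections 4.2 and 4.4 disagree on whether a patient with no qualifying alteration may enter on non-measurable liver metastases, and the response denominator does not require measurable disease

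*Combined protocol and SAP*

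**What the plan says.** **Numbered criteria (4.2).** Criterion 3 accepts "Evidence of metastatic PC on imaging (bone scan and/or CT/MRI scan"), so a bone scan alone is enough. Criterion 3a adds: "Patients with liver metastases must have biopsy proven evidence of metastatic prostate cancer in the liver". Criterion 11 begins: "Patients without liver metastases must have evidence of amplification or activating mutation of selected targets of cabozantinib". No numbered criterion asks for measurable disease.

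**Molecular eligibility (4.4).** This section first requires an alteration or overexpression of every patient. It then makes one exception: patients who miss the molecular criteria "will be allowed to enroll if they have liver metastases that meet RECIST criteria for measurable disease".

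**Link between the two.** Criterion 11 carries the pointer "See Section 4.4 for full detail", placed where it introduces the list of molecular tests.

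**Response.** The primary objective (1.2.1) is "To assess the radiographic response proportion of cabozantinib in patients with metastatic CRPC". Section 10.2 defines CR as "the disappearance of clinical and radiological evidence of all target lesions", with normal tumor markers, and defines PR by the summed diameters of the target lesions. Section 12.3.2 reports a binomial proportion of patients with CR or PR. Section 12.5.2 makes patients assessable for response after at least three cycles. Neither section mentions measurable disease at baseline.

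**Primary endpoint.** Section 12.1 states: "The primary endpoint is radiographic progression-free survival (rPFS"). It lists tumor response as secondary.

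**The concern.** The two eligibility rules give opposite answers for an identifiable type of patient in the cohort that Section 12.1 allows to reach 28 of the 30 places. Section 4.7 plans about eight sites and Section 5.2 registers patients on a signed eligibility checklist. If one site works from the numbered list and another from 4.4, the same man is enrolled at the first and refused at the second.

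The second stake is the response proportion. A patient with no measurable soft-tissue lesion anywhere has no target lesions, so he cannot be a responder under 10.2. The analysis text still counts him. The reported proportion then depends partly on how many such patients were let in, as well as on the activity of the drug.

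**Working it through.** **Step 1: apply both rules to the same patient.** Take a man with biopsy-proven liver metastases, none of them RECIST-measurable, and no qualifying alteration.

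| Rule | Result |
|---|---|
| Criterion 3a | met (biopsy proof) |
| Criterion 11 | does not apply (he has liver metastases) |
| 4.4, molecular rule | not met |
| 4.4, liver exception | not met (not measurable) |

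He is eligible under 4.2 and ineligible under 4.4. The pointer in criterion 11 does not settle this, because it sits on a requirement that applies only to men without liver metastases. Section 4.1 ties eligibility to the inclusion and exclusion criteria, which favours the numbered list.

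**Step 2: who is unscorable for response.** The two rules disagree when a patient has (a) liver metastases, (b) no alteration and (c) no measurable liver lesion. The response proportion is affected only if he also has (d) no measurable soft-tissue lesion at another site and (e) at least three cycles of treatment, as 12.5.2 requires. Nothing in 10.2, 12.3.2 or 12.5.2 then removes him from the denominator.

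**Step 3: the plan's own figure.** The only precision figure for the liver cohort is 31.1-68.9% in 12.1. It is reproduced by 0.5 ± 2 × √(0.25/28) = 0.5 ± 0.189. With 1.96 in place of 2 the result is 31.5-68.5%. This figure concerns rPFS, and the eligibility conflict does not change it.

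**Step 4: size of the effect on response.** The documents give neither the share of patients without measurable disease nor an expected response rate, so both are assumptions here. Let r be the true response rate in measurable patients and k the number of unscorable patients among N = 30 (12.2), counted as non-responders. The expected reported proportion is r × (30 − k)/30.

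| r | k = 0 | k = 3 | k = 6 | k = 12 |
|---|---|---|---|---|
| 10% | 10% | 9% | 8% | 6% |
| 20% | 20% | 18% | 16% | 12% |
| 30% | 30% | 27% | 24% | 18% |

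Here k covers every unscorable patient, including those with an alteration. The group created by the conflict between 4.2 and 4.4 is only part of it.

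**Step 5: would aligning eligibility be enough?** No. Under both sections a man with a qualifying alteration may enter with bone-only disease, or with non-measurable liver disease. He is just as unscorable, and he stays in the denominator.

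**The case against.** Several stronger readings are tempting, and the documents do not support them.

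- *Every patient admitted on non-measurable liver disease is unscorable.* Section 10.2 works on soft-tissue target lesions at any site. A man with a measurable node or lung lesion can still be CR or PR.
- *The problem covers 28 of the 30 places.* The 28 is a ceiling. It includes liver patients with measurable lesions and liver patients with an alteration. The group in conflict is a subset of unknown size.
- *A true 30% response would read about 24-27%.* That follows from assuming 3 to 6 unscorable patients among 28 (0.30 × 25/28 = 26.8%; 0.30 × 22/28 = 23.6%). Neither the share nor the 30% is in the documents, and 12.3.2 does not limit the proportion to liver patients.
- *The primary analysis is compromised.* Section 12 makes rPFS primary. Under 10.6, rPFS counts progression in bone or soft tissue, or death, and needs no measurable lesion at baseline.
- *Correcting the eligibility wording protects the response proportion.* Step 5 shows that it does not.

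It is also fair to say that criterion 11 does send readers to 4.4, that the content of the checklist is not shown, and that central registration asks for source documents verifying eligibility. Finally, 12.3.2 only estimates the proportion. There is no response threshold for a shift of a few points to cross, and at 6/30 the exact 95% interval is already 7.7-38.6%.

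These points limit the consequence. They do not remove the contradiction, because central verification cannot apply one rule while the protocol states two.

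**Conclusion.** The contradiction stands in the current text and decides who may enter, so it should be resolved. Its effect on the response proportion is real in direction: patients with no measurable lesion at any site can only lower it. Its size cannot be determined from the documents. Under the assumed inputs above, 3 to 6 unscorable patients of any origin lower the expected proportion by 1 to 2 points if the true rate is 10%, and by 3 to 6 points if it is 30%. This matters most if response is the primary measure, as 1.2.1 says, and less if rPFS is, as Section 12 says. The result rests on counting unscorable patients as non-responders. The plan's wording implies this but does not state it.

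**What to change.** 1. **Eligibility.** Carry the 4.4 condition into criteria 3a and 11, so that a patient without a qualifying alteration needs biopsy-proven liver metastases that are RECIST-measurable. Put the same wording on the eligibility checklist.
2. **Response population.** In 12.3.2 and 12.5.2, restrict the CR/PR proportion to patients with measurable soft-tissue disease at baseline, or report it both in those patients and in all assessable patients. This step is needed because step 1 does not reach patients who enter on an alteration.

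The cost is one wording amendment. A few patients whom 4.4 already excludes will not be enrolled. The response denominator may be somewhat smaller: if 6 of 30 were non-measurable, the exact 95% interval near 20% would go from 7.7-38.6% (6/30) to 7.1-42.2% (5/24).
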